For secondary outcomes, we will assess change in patient-reported outcome scores from baseline (at time of enrollment) to 6-months (post-enrollment). For satisfaction variables with responses "never", "sometimes," "usually," or "always" we will report results as the proportion of participants who respond "always" at 6-months post-enrollment compared to all other responses. For satisfaction variables with responses, "strongly disagree," "disagree," "neither agree nor disagree," "agree," or "strongly agree, we will report results as the proportion of participants who respond, "strongly agree." For overall health and overall mental and emotional health variables, responses are scores that range from 0 to 5, with lower scores indicating "very good" or "excellent" health and higher scores indicate poorer overall health. We will report results as the proportion of participants who respond, "very good" or "excellent." Missing data will not be imputed in any case. We will utilize GEE to compare changes between groups overtime from baseline (time of enrollment) to 6-months post-enrollment using GEE models with a term for an interaction between the treatment group and time (month) and clustered within person.

We will compare survival using Kaplan Meier methods and the risk of death for both groups after randomization using Cox proportional hazards regression models. All analyses will be adjusted for covariates that are found to be imbalanced between study groups, such as age, race/ethnicity, cancer stage and cancer diagnosis.

Relevant subsets of the above metrics may be measured on patients by cancer diagnosis and stage.

Sample Size Considerations

The sample size of 128 participants (64 randomized to the intervention group and 64 randomized to the control group) provides greater than 90% power to detect a 55% or greater difference in acute care use risk at 6-months follow-up. The anticipated effect size was based on our prior studies [11, 13, 18] and feedback by the oncology clinicians at St. Jude's Crosson Cancer Institute. Power calculations will not be generated for our secondary outcomes as these are considered exploratory. Statistical significance of secondary outcomes is for trends only and not represented in this sample size calculation.

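### The two graded health items have only one stated result, a two-category share, so changes below *very good* do not register and precision is lost

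*Combined protocol and SAP*

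**What the plan says.** The relevant text is the paragraph on patient-reported secondary outcomes in section 5.2.

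- It opens with graded outcomes: "we will assess change in patient-reported outcome scores from baseline (at time of enrollment) to 6-months (post-enrollment".
- It describes the overall health and the overall mental and emotional health items in these terms: "responses are scores that range from 0 to 5, with lower scores indicating" the better health categories.
- It then gives the result to be reported for these two items: "We will report results as the proportion of participants who respond, 'very good' or 'excellent".
- Agreement-type satisfaction items are treated in the same way ("we will report results as the proportion of participants who respond, 'strongly agree"), and frequency-type items are cut at the top response.
- The model sentence reads: "We will utilize GEE to compare changes between groups overtime from baseline (time of enrollment) to 6-months post-enrollment using GEE models", with a group-by-time interaction and clustering within person. It names no outcome form, family or link.
- On missing data: "Missing data will not be imputed in any case".
- On status: "Power calculations will not be generated for our secondary outcomes as these are considered exploratory".

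No reason for the cut, no graded sensitivity analysis and no baseline distribution is given. Section 5.2 refers to an attached detailed analysis plan; no separate one is in the text available for this review.

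**The concern.** Improving overall health and emotional and mental health is a stated secondary aim (section 1.0). The instrument records several grades, but the stated result separates patients only at one boundary, between *very good* and the category below it. A patient who moves up or down among the lower categories looks unchanged. So does one who moves between *very good* and *excellent*.

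There are at most 64 patients per arm, and fewer will be observed at 6 months because deaths are expected and missing values are not imputed. Section 5.3 says the trial expects to obtain point estimates. A study of that kind has good reason not to discard precision it has already collected. The loss is largest if few patients start in the top two categories.

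**Working it through.** **No figure to reproduce.** The plan's only power statement (above 90%, sections 5.2 and 5.3) concerns acute care use and has no bearing here.

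**Inputs.** From the documents: graded items, a cut at the top two categories, and at most 64 per arm. Assumed: five ordered levels, a common odds ratio (OR) of 2.5, two-sided alpha 0.05, 50 per arm observed at 6 months, and the control distributions in the table (best to worst category).

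**Step 1: information kept by the cut.** Under proportional odds, information on the log odds ratio is proportional to 1 − Σp̄³, where p̄ is the average of the two arms' category proportions.

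Example, 20% of controls in the top two:
- Top-two share in the intervention arm: odds 0.25 × 2.5 = 0.625, so 0.625/1.625 = 38.5%.
- Averaged proportions: 0.083, 0.209, 0.315, 0.247, 0.145. The sum of cubes is 0.059, so the full scale gives 0.941.
- Cut: averaged share 0.292, so 1 − 0.292³ − 0.708³ = 0.621.
- Kept: 0.621/0.941 = 66%.

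**Step 2: power.** V = [n²N/(3(N+1)²)] × (1 − Σp̄³), with n = 50 and N = 100, so the bracket is 8.169. Power = Φ(ln 2.5 × √V − 1.96).
- Full scale, 20% case: V = 7.69; 0.916 × 2.772 − 1.96 = 0.58; power 72%.
- Cut: V = 5.07; 0.916 × 2.252 − 1.96 = 0.10; power 54%.

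| Controls in top two | Assumed control distribution (%) | Information kept | Power by formula, full vs cut | Simulated power, full vs cut |
|---|---|---|---|---|
| 10% | 2/8/30/35/25 | 44% | 71% vs 38% | 70–71% vs 37–40% |
| 20% | 5/15/30/30/20 | 66% | 72% vs 54% | 71–72% vs 54–56% |
| 40% | 10/30/30/20/10 | 81% | 71% vs 62% | 69–71% vs 63–65% |
| 50% | 15/35/30/15/5 | 78% | 71% vs 60% | 69–70% vs 60–61% |

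The simulations compare a rank-sum test with a two-proportion z-test; the ranges are across repeated runs. With all 64 per arm observed, power is about 82% on the full scale, against 44% (10% share), 63% (20%) and 70–73% (35–50%) with the cut.

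Using control proportions alone in step 1 gives 30%, 51% and 77% for the first three rows. That is the no-effect case and overstates the loss at an odds ratio of 2.5.

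**Step 3: which changes register.** Suppose each patient able to move one category up or down is equally likely to do so. The share of such moves that crosses the cut is (proportion in *very good* + proportion just below it) ÷ (proportion able to worsen + proportion able to improve):
- 10%: (0.08 + 0.30)/(0.75 + 0.98) = 22%
- 20%: (0.15 + 0.30)/(0.80 + 0.95) = 26%
- 40%: (0.30 + 0.30)/(0.90 + 0.90) = 33%
- 50%: (0.35 + 0.30)/(0.95 + 0.85) = 36%

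For changes of any size, a latent-normal simulation (within-person correlation 0.5–0.7, mean worsening 0–0.5 SD) gives 17–53% crossing.

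**Step 4: the cut itself.** A range of 0 to 5 has six values, and section 5.2 does not say which of them mean *very good* and *excellent*. The numeric cut is therefore undefined.

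**The case against.** The strongest reply is that section 5.2 speaks of *reporting* a proportion, while separately promising "we will assess change in patient-reported outcome scores from baseline" and a GEE comparison of changes whose outcome is not named. A reader might infer that the graded scores are never modelled. The text does not establish that, and the attached detailed plan may settle it. What stands is that the share is the only result format stated. If the score was meant, section 5.2 still needs a sentence saying so.

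Three other stronger readings are tempting and are not supported.

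- *Most changes are missed because these patients sit near the bottom of the scale.* No baseline distribution is given. Eligibility (section 3.2) includes stage II rectal, stage III colon and limited-stage small cell lung cancer, and nothing is said about where emotional health lies. With half the patients starting in the top two and correlation 0.5, 52–53% of changes cross the cut.
- *A finding of no difference would be uninterpretable.* A difference in proportions with its interval still means what it says. The plan calls these outcomes exploratory and reads their significance as trends only, and section 5.3 accepts that significance may not be reached.
- *The satisfaction scales should be averaged too.* The response format and scoring of the six-question decision scale are not given, so that does not follow.

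It is also fair that a prespecified top-category share is a legitimate and readable summary, and that the calculation above is cross-sectional whereas the plan's model is longitudinal.

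**Conclusion.** The point holds as a modest, inexpensive improvement. On the natural reading of section 5.2, the two health items are compared between arms as a binary share, and this costs power in every scenario tried. At an odds ratio of 2.5 and 50 per arm, the cost is roughly 30 percentage points if 10% of controls are in the top two, 15–18 points if 20%, and 5–11 points if 40–50%. The information kept is about 44%, 66% and 78–81%.

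These sizes rest on five levels, proportional odds and assumed control distributions, none of which is in the documents. The direction does not depend on which of the tried shares applies; the size does. The outcomes are exploratory and unpowered, so the trial's main conclusion is not affected.

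**What to change.** In section 5.2:

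1. Name the graded response as the between-arm outcome for overall health and for overall mental and emotional health. Use GEE with the group-by-time interaction already planned, either ordinal (proportional odds) or on the mean score, and state the family and link.
2. State which score values correspond to *very good* and *excellent*, and reconcile the 0-to-5 range with the response categories.
3. Keep the *very good* or *excellent* share by arm and time point as a descriptive result.

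This point asks for no change to the six-question decision scale.

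The cost is a few sentences and one changed model for each of the two items, on data already collected. The downside is that an odds ratio or mean difference is slightly less intuitive than a percentage, which is why the percentages stay.

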3.0 STUDY ENROLLMENT AND PARTICIPANT ELIGIBILITY

3.1 Study Enrollment

Location

Patients will be recruited from the oncology clinics at St. Jude Hospital in Fullerton, CA.

Enrollment Procedures

Each week, the site PI and study staff will receive a list of potential patients. After the site PI and study staff conduct proper screening (see below section titled "Screening Procedures" for specific details), the staff will create a list of eligible patients and their primary oncology appointment times. At the patient's oncology appointment, the oncologist will present the study and initiate the consent procedure (see below section titled "Consent Procedures" for specific consent details).

Screening Procedures

The Site PI and staff will utilize the following documents and procedures to screen for patients who fit the inclusion criteria listed in 3.2

- Diagnosis (ICD-9) codes
- Provider Referrals (request for oncology consultation)
- Pathology results (must be positive for malignancy)
- Biopsy requests
- Abnormal test results (mammograms, colonoscopies, imaging results)

Screen failures will not be included in the study data. The PI will keep a record of history and reasons for screen failures; however, any patient information gathered during this process will be destroyed.

Consent Procedures

The oncologist will refer eligible patients to the program. The program manager or the primary oncologist will introduce will obtain consent from eligible patients at the patient's primary oncology appointment following advanced cancer diagnosis. The program manager or the oncologist will introduce the research project and provide a consent form document describing the project with sufficient information to potential participants. Patients will be provided adequate time to make an informed decision regarding their participation. Participants must sign an IRB approved informed consent document prior to participation in any study specific procedure. The participant will receive a copy of the signed and dated consent form document. The original signed informed consent document will be retained in the research file. Patients who refuse participation or have no capacity for decision-making will not be included in the study.

If a patient consents, patients will be provided a welcome letter with basic information and contact phone numbers for the project.

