4.0 MATERIALS AND METHODS

After a patient consents, the patient will be registered and entered into the project database and assigned an identification number. The subject's identification number will be used on all subject-specific documents and research-related forms.

During registration, patients will be randomized to two arms (Arm A: Usual Care Arm B: Health Care Coach Intervention). Specifically, the patients will be randomized into two arms by cancer type.

All patients will be surveyed over the course of the study regarding patient experience with care, patient satisfaction and overall health status and emotional and mental health status (using the CG-CAHPS: Clinician and Group Consumer Assessment of Healthcare Providers and Systems), advanced care planning, and symptom assessments (using the ESAS: Edmonton Symptom Assessment Scale) and healthcare use. A member of the project team, excluding the Health Care Coach, will administer the assessments and conduct an electronic health record review of all health care use at baseline, 3, 6, 9 and 12 months post-enrollment. Participants will provide consent for health record review at external facilities by signing a health release authorization form at each of the outcome assessment time periods. The symptom assessments will be administered at baseline for each patient in the intervention and control. Participant information should be entered into the local databases within 7 calendar days.

Arm A: Usual Care (Control) / No Intervention
 Patients in this arm receive "usual" care from their care team.

Arm B: Health Care Coach Arm / Intervention Group

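### The patient-reported outcomes are compared on change from baseline without using the baseline response for adjustment, which probably costs precision; the GEE should be written out with a common baseline.

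*Combined protocol and SAP*

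**What the plan says.** Section 5.2 sets the target for the patient-reported outcomes: "we will assess change in patient-reported outcome scores from baseline (at time of enrollment) to 6-months (post-enrollment"). The arms are to be compared "using GEE models with a term for an interaction between the treatment group and time (month) and clustered within person". The items are dichotomised. For the frequency-scaled satisfaction items, "we will report results as the proportion of participants who respond 'always' at 6-months post-enrollment compared to all other responses". The agreement items and the two health-status items are likewise reduced to a proportion in the top category or categories, with no time point named for that summary.

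A baseline response is planned. Under section 4.0 the project team will administer the assessments and "conduct an electronic health record review of all health care use at baseline, 3, 6, 9 and 12 months post-enrollment".

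On covariates, section 5.2 says "All analyses will be adjusted for covariates that are found to be imbalanced between study groups, such as age". Its other examples are race/ethnicity, stage and diagnosis; the baseline patient-reported response is not among them. It also says "Missing data will not be imputed in any case", and of these outcomes, "Power calculations will not be generated for our secondary outcomes as these are considered exploratory".

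For this GEE the section does not state whether there is a group main effect, whether month is linear or categorical, or which working correlation applies. For the 6-month count model it does name an independence structure.

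**The concern.** In a randomized trial the expected baseline difference between arms is zero. A model that makes baseline an outcome row and gives each arm its own baseline mean estimates a baseline difference and subtracts it from the 6-month difference. Unless baseline and follow-up are strongly correlated, this mostly adds noise. The same data, with baseline used as a covariate or with the arms held to a common baseline, give a tighter estimate.

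Satisfaction, overall health, and emotional and mental health are the trial's stated secondary aims. There are at most 64 patients per arm, the population has advanced cancer and some will die before month 6, and missing responses are not imputed. Section 5.3 says the trial expects to deliver point estimates that may not reach significance, so the width of the intervals is much of what the trial can offer.

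A smaller point concerns reporting. For the frequency-scaled items the reported figure is a 6-month proportion, while the test addresses a difference in change. A p-value from that test, printed beside the 6-month proportions, would answer a different question.

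**Working it through.** **The plan's own figure.** There is none to reproduce. The only power statement (128 patients, over 90%) concerns acute care use. No correlation, standard deviation, effect size or power is given for the patient-reported outcomes.

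**Inputs.** From the documents: 64 patients per arm, assessments at months 0, 3 and 6 within the 6-month window, and the change contrast. Assumed: equal variance s² at baseline and 6 months, and correlation r between 0.2 and 0.7.

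**Formulas (continuous case).** The variances below are per patient; each estimate's variance is this figure times 2/n for n patients per arm.

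- Change from baseline: 2(1-r)s²
- 6-month value, baseline ignored: s²
- 6-month value, adjusted for baseline: (1-r²)s²

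Adjusted over change is (1-r²)/[2(1-r)] = (1+r)/2. The precision lost by the change contrast is therefore 1-(1+r)/2 = (1-r)/2. The narrowing of the interval available from adjustment is 1-√[(1+r)/2]. The number of patients whose adjusted analysis would match the change analysis of all 128 is 128(1+r)/2.

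| | r=0.2 | r=0.5 | r=0.7 |
|---|---|---|---|
| Change, 2(1-r) | 1.60 | 1.00 | 0.60 |
| Baseline ignored | 1.00 | 1.00 | 1.00 |
| Adjusted, 1-r² | 0.96 | 0.75 | 0.51 |
| Adjusted / change | 0.60 | 0.75 | 0.85 |
| Precision lost by change | 40% | 25% | 15% |
| Narrowing available | 22.5% | 13.4% | 7.8% |
| Equivalent patients (of 128) | 77 | 96 | 109 |

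The loss is 50% at r=0 and 10% at r=0.8. Below r=0.5 the change contrast is less precise than discarding baseline altogether.

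**Binary check.** The planned endpoints are dichotomised, so the comparison was repeated with a logistic GEE. The settings were 64 per arm, months 0, 3 and 6, exchangeable working correlation, 50% prevalence, no missing data and 250 simulated trials per scenario. The full interaction model (with group main effect) was compared with the same model under a common baseline:

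| Binary correlation, baseline to month 6 | 0.19 | 0.33 | 0.50 | 0.64 |
|---|---|---|---|---|
| Variance ratio, common baseline / full | 0.64 | 0.60 | 0.78 | 0.81 |
| (1+r)/2 | 0.59 | 0.67 | 0.75 | 0.82 |

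The loss is about 20% to 40%, in line with the formula apart from simulation noise. Coding month as linear or as a category made almost no difference to the variance of the full model.

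**What this can mean for power.** This is an illustration under assumed inputs: 50 responders per arm, 50% in the top category at baseline in both arms, 50% versus 70% at 6 months, and 4,000 simulated trials per correlation. At latent correlations of 0.2, 0.4 and 0.6:

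- interaction test: 36%, 39% and 48%
- logistic model adjusted for baseline: 54%, 56% and 61%
- 6-month comparison ignoring baseline: 55%, 54% and 54%

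Type I error was about 4.5% to 5.5% for the first two and about 6% for the third. At latent correlation 0.8 the interaction test had 61% power and the adjusted model 70%.

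**Dependence on the unstated model.** With no group main effect and month as a category, the arms share a baseline. Under a non-independence working correlation that model is close to baseline adjustment, and little is lost. Under independence its 6-month contrast is simply the 6-month comparison ignoring baseline (the second row of the first table), which forgoes r² of the adjusted precision: 4%, 25% and 49% at r=0.2, 0.5 and 0.7.

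**The case against.** The strongest reply is that the model is inferred. Section 5.2 mentions an interaction term and clustering, nothing more. A version without a group main effect and with a suitable working correlation would lose little. The heading of section 5.2 also refers to an attached detailed analysis plan, which is not in the text available here and may settle the matter. This stands, so the loss is stated conditionally. It does not remove the need to write the model out, because the section as it reads supports forms of quite different precision.

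The documents also give no correlation. A reader might take 40% as the trial's loss, or as its maximum. It is neither: it belongs to r=0.2, the limit is 50% at r=0, and the loss is 15% at r=0.7. It is also a loss of inverse variance; the interval at r=0.2 would narrow by 22.5%. One might argue for a low r because consent is obtained at the "primary oncology appointment following advanced cancer diagnosis", before most of the care to be rated. That reasoning applies only to satisfaction, not to overall or emotional health. Section 3.2 also admits patients with recurrent cancer, who may already have care to rate.

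The power illustration uses low correlations. For a 50% endpoint, latent values of 0.2, 0.4 and 0.6 correspond to binary correlations of about 0.13, 0.26 and 0.41 (from (2/π)·arcsin r), all below 0.5. Most of its gain comes from not subtracting baseline rather than from adjusting for it. Both points stand.

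Adding baseline to a logistic model changes the odds ratio from marginal to conditional. This also stands, and it determines the form of the remedy.

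Finally, these outcomes are labelled exploratory, with significance for trends only. That limits the consequence. It is not a reason to accept wider intervals when the baseline is already being collected.

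**Conclusion.** The point holds in conditional form. The plan tests change from baseline and prespecifies neither adjustment for the baseline response nor a common baseline. If the GEE includes a group main effect, the contrast is less precise than a baseline-adjusted one at any correlation below 1, given equal variances at the two visits. The size is 15% to 40% of precision for r from 0.7 to 0.2. That range is an assumption, because the documents state no correlation; the binary simulation supports a similar range.

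A reader might infer that the planned analysis is biased or inflates false positives. Neither follows: the issue is efficiency only, and simulated type I error for the interaction test was close to nominal. A reader might also infer that every patient-reported result will carry a mismatched p-value. The text ties only the frequency-scaled items to month 6, and 6-month proportions may properly be shown beside a longitudinal test if the p-value is not attached to their difference. No conclusion on the primary outcome depends on this point.

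**What to change.** In section 5.2, replace the sentence on the patient-reported GEE with a full specification:

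- Outcome rows: the dichotomised responses at baseline, 3 and 6 months, clustered within patient.
- Terms: visit as a category and arm-by-visit terms at 3 and 6 months only. There is no group main effect, so the arms share one baseline mean.
- A working correlation other than independence (for example exchangeable), with robust standard errors.
- Effect: the arm contrast at 6 months, reported as a difference in proportions or a marginal odds ratio, with its confidence interval.

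This form also keeps patients whose baseline response is missing. Alternatively, model the follow-up responses with the baseline response as a covariate and report standardised 6-month proportions by arm, rather than the conditional odds ratio. Under either option the reported 6-month figure and the test refer to the same quantity.

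If the attached detailed analysis plan already gives the model, section 5.2 should be brought into line with it. The cost is a few lines of analysis text, with no new data, visits or patients.

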3.2 Participant Criteria

Inclusion criteria

- 1. Newly diagnosed patients for the following conditions.
 - Colon cancer stage III and IV
 - Rectal cancer stage II, III, IV
 - Glioblastoma multiforme (brain) -- no stage
 - Non-small cell lung cancer stage IIIA, IIIB, IV
 - Small cell lung cancer, limited stage and extensive stage
 - Castration-resistant prostate cancer
 - Head and neck cancer stage III and IV
 - Gastric cancer stage III and IV
 - Esophageal cancer stage III and IV
 - Pancreatic cancer stage II,III, IV
 - Renal cell carcinoma, stage IV
 - Breast cancer, stage IV, if triple negative ER/PR/H2N negative or on systemic chemotherapy
 - Sarcoma, stage IV
 - Bladder carcinoma, stage IV
 - Acute myeloid leukemia
 - Melanoma, stage III and IV
 - Ovarian cancer, stage III and IV
 - High Grade MDS

Eligibility also includes patients with recurrent cancer of any diagnosis.

- 2. The patients must be 18 years or older.
- 3. Patients must have the ability to understand and willingness to sign a written informed consent document.
- 4. Patient must have ongoing oncologic needs and plan to receive all care at the study institution and not already be in hospice or home-care.

Exclusion Criteria

The disease must be *newly* diagnosed or patients with recurrent disease of any cancer diagnosis. Patients must not already receive hospice services and palliative care.

Criteria for Removal from Study

Any patients or families of patients in the intervention arm who withdraw consent will be removed from the study. Upon removal, usual care will be restored for these patients.

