3.3 Enrollment

The target number of subjects at the site is 128. Patient enrollment is anticipated to begin upon study approval and continue until 128 participants have enrolled.

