5.2 Analysis Plan (see Detailed Statistical Analysis Plan Attached)

All patients will be included in the analysis based on their randomization assignment at time of enrollment. The unit analysis will be completed at the participant-level. We will conduct descriptive statistics to evaluate balance between demographic (i.e., sex, age, race/ethnicity) and clinical variables (i.e., stage of cancer, diagnosis of cancer) between both the randomized and control groups. To assess our primary outcome of the effect of the intervention on acute care use within 6-months post-enrollment we will assess % of patients with acute care use. We will create a (composite measure for acute care use that includes both ED visits and hospitalizations. To compare risk of acute care use (composite measure) and individual ED and hospital use within 6 months post-enrollment, we will use Cox regression models. We will also compare counts of total ED visits and hospitalization (composite measure of acute care use) within the first 6 months, using General Estimating Equation with Poisson family, log link, and independent correlation.

For secondary outcomes of ED and hospital use within 12 months, we will compare use using GEE models. We will compare counts of total ED visits and hospitalization (composite measure of acute care use) within 12 months, using General Estimating Equation (Poisson) with an offset term for length of follow-up. To compare goals of care discussion and documentation, Advance Directive

documentation, Physician Order for Life Sustaining Treatment documentation, Chemotherapy, Radiation, Surgery, hospice, and palliative care within 12 months, we will use GEE models to compare odds of documentation or use across groups. For end-of-life health care use, we, we will compare any ED use and hospital use prior to death (30 days prior) and proportion of participants with palliative care and hospice use using the models described above among participants who died during the 12-month study.

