Interim analyses every 6 months will evaluate point estimates and trends to inform refinements to the protocol. Descriptive statistics and exploratory data analyses will be conducted as needed to evaluate protocol process measures with key outcomes identified.

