5.3 Sample Size

The goal is to reduce acute care use. Based on data from St. Jude Hospital, the mean number of acute care visits per member per year is 1.45. Local site oncologist in the pre-review assessment anticipated at least a 55% difference in risk of acute care use among participants in the intervention group as compared to the control group. For this trial, we estimated that a sample size of 128 participants would have at least 90% power with a 2-sided type I error rate of 0.05 to detect at least a

55% difference in risk of acute care use in the intervention group compared with the control group based on effect sizes from our ongoing VA pilot and other pilot studies. For this trial, we expect to obtain point estimates with an understanding that we may not reach significance in this study.

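### Does the stated power above 90% fail because it needs every patient to have the same visit rate?

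*Combined protocol and SAP*

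**What the plan says.** Section 5.2 (Analysis Plan) defines the 6-month primary comparison as follows: "we will assess % of patients with acute care use", using a "composite measure for acute care use that includes both ED visits and hospitalizations", with risk compared by Cox regression. Its sample size paragraph states that 128 patients, 64 per arm, "provides greater than 90% power to detect a 55% or greater difference in acute care use risk at 6-months follow-up". Section 5.3 adds the two-sided 0.05 level and the baseline figure ("the mean number of acute care visits per member per year is 1.45"). It attributes the effect size to pilot work and concedes that significance may not be reached.

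Section 3.2 lists many diagnoses and stages and then widens the entry: "Eligibility also includes patients with recurrent cancer of any diagnosis". Section 4.0 says that "the patients will be randomized into two arms by cancer type", and section 5.2 adjusts analyses for covariates found to be imbalanced, naming cancer stage and diagnosis among its examples. Under section 3.3, enrollment is to "continue until 128 participants have enrolled". Section 5.2 also says: "Interim analyses every 6 months will evaluate point estimates and trends to inform refinements to the protocol".

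The control-arm percentage behind the power is not given in the text available. The heading of 5.2 points to an attached detailed analysis plan that is not in that text and may give it.

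**The concern.** Power for a comparison of percentages depends on the control percentage, but the plan gives a mean number of visits. A few patients with many visits can produce the same mean as many patients with one visit each, and the first pattern leaves fewer patients with any event. With visits evenly spread over the year, equal rates for everyone give the highest possible percentage, and any variation lowers it. The eligible population is visibly mixed. A further downward pull is possible if an emergency visit and the admission that follows it were counted as two visits in the 1.45.

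If the control percentage is lower than the plan implies, 128 patients yield too few first events and the chance of missing a true 55% reduction exceeds 10%. Enrollment stops at a fixed number, and the 6-monthly looks carry no target for pooled events.

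**Working it through.** **Inputs from the documents.** 64 per arm and a 55% lower risk (5.2); two-sided 0.05 and 1.45 visits per year (5.3). The 55% is read as a risk ratio of 0.45. All other inputs below are assumptions.

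**1. The plan's own figure.** Evenly spread visits give m = 1.45/2 = 0.725 per 6 months. With one common Poisson rate:

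- Control risk P0 = 1 − exp(−0.725) = 0.516; intervention risk P1 = 0.45 × 0.516 = 0.232.
- Two proportions: difference 0.284, standard error 0.0855 under the null and 0.0818 under the alternative. Power = Φ[(0.284 − 1.96 × 0.0855)/0.0818] = 92.2%.
- Cox model: hazard ratio = ln(1 − P1)/ln(1 − P0) = 0.364. Expected events = 64 × (0.516 + 0.232) = 47.9, against 41.2 needed for 90%. Power = Φ[√(47.9/4) × |ln 0.364| − 1.96] = 93.7%. Simulated log-rank power is about 93%.

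The stated figure reproduces.

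**2. Variation between patients, visits still evenly spread.** For gamma-distributed rates with shape k, P0 = 1 − (1 + m/k)^(−k), and the variance of the counts is (1 + m/k) times the mean.

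| Variance / mean | P0 | Two proportions | Schoenfeld | Simulated log-rank |
|---|---|---|---|---|
| 1.00 | 51.6% | 92.2% | 93.7% | 92.6% |
| 1.36 (k = 2) | 46.1% | 86.9% | 89.2% | 88.0% |
| 1.73 (k = 1) | 42.0% | 81.9% | 84.7% | 83.3% |
| 2.45 (k = 0.5) | 36.1% | 73.0% | 76.5% | 74.7% |

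Power of 90% needs P0 of at least 49.1% (two proportions) or 46.9% (Schoenfeld). These are reached at a variance of 1.15 and 1.30 times the mean. No section gives a variance. With equal rates but an assumed 20% of double-counted visits, P0 = 44.0% and power is 84.4% / 87.0%.

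**3. Timing of visits.** Patients enter at new diagnosis or recurrence, so visits need not be evenly spread.

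- At k = 2, if 52% of the year's visits fall in the first 6 months, m = 0.754, P0 = 47.3% and Schoenfeld power is 90.3%. At 56%, m = 0.812, P0 = 49.4% and the two formulas give 90.3% (two proportions) and 92.2% (Schoenfeld).
- At k = 1 the share must be 61% (Schoenfeld) or 66.5% (two proportions).
- In the other direction, a 40% share gives Schoenfeld power of 87.0% with equal rates, 82.0% at k = 2 and 77.4% at k = 1.

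**4. Balance by cancer type.** Step 2 ignores the design. Suppose half the patients have 0.58 and half 2.32 visits per year (mean 1.45). Then P0 = 1 − ½[exp(−0.29) + exp(−1.16)] = 46.9%. With a marginal risk ratio of 0.45, simulated log-rank power is:

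- 88.8% with groups not balanced and the analysis not stratified;
- 90.1% with groups balanced across arms;
- 93.0% with groups balanced and the analysis stratified.

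This assumes that the strata capture the rate differences.

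**5. What a remedy would do.** One rule would count pooled first events once 80 patients have 6-month data, and extend enrollment to 156 (28 more) if fewer than 44 events are projected at 128. In simulation it extends 29% of trials when P0 is 51.6% and the 55% effect is true. At k = 1 it still reaches only 88.8%. It also responds to success: at P0 = 51.6% and a true 70% reduction, expected events are 64 × 0.516 × 1.30 = 42.9, below the cut-off, although 128 patients are already ample.

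**The case for a change.** The strongest case for acting is that the percentage matters, the plan does not give it, and the stated power reproduces at equal rates with only 2 to 4 points to spare. Identical rates are hard to believe in a population that mixes stage II rectal cancer with glioblastoma, acute leukemia and recurrent disease. The break-even variance, 1.15 to 1.30 times the mean, is low. Writing down the control percentage would cost a sentence.

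Much of this stands as arithmetic, and the missing percentage is real. But the evidence for variation is diagnosis and stage. Diagnosis enters the randomization, and both are named for adjustment, so variation of that kind is largely recovered in step 4. Adjustment is conditional on imbalance, so the recovery is not guaranteed. The 83% to 88% applies to differences that diagnosis and stage do not explain, and the documents offer nothing on those. It also requires even spread over the year, which is equally undocumented.

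A separate question of wording remains. If the 55% were a hazard ratio of 0.45, equal rates would give 64 × (0.516 + 0.278) = 50.8 events and power of 81.2%. Both 5.2 and 5.3 speak of a difference in risk, so the risk-ratio reading is the natural one, and under it the claim reproduces.

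**Conclusion.** No change is needed. At the only documented inputs the power is 92.2% to 93.7%, which agrees with the plan. A shortfall to about 83% to 88% requires three things together: an assumed variance of 1.36 to 1.73 times the mean, visits spread evenly over the year, and rate differences that balance and adjustment by cancer type do not capture. Altering the first two moves power in either direction, and the documents do not settle which case applies.

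The unstated control percentage is a reporting gap. Filling it would leave the endpoint, the Cox model and the 128 patients as they are. Adding an enrollment extension would commit up to 28 more patients against a deficit that no stated figure shows. The consequence is bounded as well: Appendix A titles the study a pilot test, section 5.3 accepts that significance may not be reached, and point estimates are reviewed every 6 months, though without a pooled event target.

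This conclusion rests on reading the 55% as a risk ratio and on taking the 1.45 as relevant to the control arm, which section 5.3 does not state outright.
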